6.1.2 Treatment period(s)

Spesolimab will be administered [REDACTED] in the clinic.

If deemed necessary by the treating physician (i.e. if the flare symptoms persist), [REDACTED] spesolimab may be administered [REDACTED] after the initial [REDACTED].

IRT transactions are required to obtain all medication kit number assignments. Dates and times of [REDACTED] will be recorded in the patient's records and eCRF.

6.1.3 Follow up period and program completion

Patients will visit the treating physician at approximately week [redacted], week [redacted] and week [redacted] after [redacted] drug administration. If the patient requires [redacted] of spesolimab, visits will be re-scheduled based on the date of the last [redacted], i.e., patients will visit the treating physician at approximately week [redacted], week [redacted], week [redacted], and week [redacted] after initial dose of spesolimab. Additional visits within the [redacted]-week follow-up period can be planned according to standard clinical practice. Visits not including the mandatory presential visits at screening (baseline) and [redacted] week after (any) administration of spesolimab, may also be conducted by phone or video if judged appropriate by the treating physician. At all visits any new or changes in previously reported AEs and concomitant therapies will be recorded in the patient's chart and eCRF.

Patient's participation in the program will end after conclusion of the [redacted]-week follow-up period after the last [redacted] / drug administration. The Trial (Program) Completion eCRF page will be completed at this time.

A patient will be considered lost to follow-up if the treating physician is not able to contact the patient despite multiple attempts. Every effort must be made to contact the patient and be documented in the patient's chart.

[figure not shown]
If a patient experiences a new GPP flare (following the resolution of a previous flare with spesolimab treatment) after the [redacted]-week follow-up period, the patient may re-enter in the program with the same patient number and be treated again with spesolimab, providing eligibility criteria are still met and the overall program is still running. The same dosing and follow-up requirements apply as for the previous flare.

In the situation that a patient experiences a new GPP flare within the [redacted]-week follow-up period and the physician wishes to treat this new flare with spesolimab, eligibility needs to be assessed and agreed upon with the BI clinical team.

Then, in case of re-entry due to a new GPP flare within the [redacted]-wks follow-up period, the patient will end the current follow-up period, and restart the program from the screening for eligibility. If eligibility criteria are met, and permission from BI is granted (see above), the patient can be treated again to receive a new dose of spesolimab. After [redacted], the patient is followed-up for [redacted]-weeks after the latest dose of spesolimab. Also for this scenario, after [redacted] week, a [redacted] dose of spesolimab can be administered, if deemed necessary by the treating physician.

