3.2 SELECTION OF PROGRAM POPULATION

3.2.1 Main diagnosis for program entry

Participation in this program will be available to patients with GPP who meet the eligibility requirements specified in section [3.2.2](#) and section [3.2.3](#). Owing to the nature and objectives of this program, no recruitment goals or limits apply.

Patients previously enrolled in this program presenting with a new episode of a GPP flare must be re-evaluated and meet eligibility criteria to receive new treatment with spesolimab.

Please refer to section [8.3.1](#) (Source Documents) for the documentation requirements pertaining to the in- and exclusion criteria.

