3.2.3 Exclusion criteria

1. Women who are pregnant, nursing, or who plan to become pregnant while in the program.
 - a) Women who stop nursing before study drug administration do not need to be excluded from participating; they should refrain from breastfeeding for 16 weeks after the last spesolimab [REDACTED].
2. Severe, progressive, or uncontrolled hepatic disease, defined as >3-fold Upper Limit of Normal (ULN) elevation in AST or ALT or alkaline phosphatase, or >2-fold ULN elevation in total bilirubin.
3. Active systemic infections (fungal and bacterial disease) during the last 2 weeks prior to drug administration, as assessed by the treating physician.
4. Increased risk of infectious complications (e.g. recent pyogenic infection, any congenital or acquired immunodeficiency (e.g. HIV), past organ or stem cell transplantation), as assessed by the treating physician.
5. Relevant chronic or acute infections, including active tuberculosis (TB), HIV infection or viral hepatitis at the time of drug administration.
 - a) Patients should be evaluated for TB infection prior to initiating treatment with spesolimab.

¹A woman is considered of childbearing potential (WOCBP), i.e. fertile, following menarche and until becoming post-menopausal unless permanently sterile.

Permanent sterilisation methods include hysterectomy, bilateral salpingectomy and bilateral oophorectomy.

Tubal ligation is NOT a method of permanent sterilisation.

A postmenopausal state is defined as no menses for 12 months without an alternative medical cause.

b) Anti-TB therapy should be considered, in accordance with local guidelines, prior to initiating spesolimab in patients with latent TB or a history of TB.

6. History of allergy / hypersensitivity to systemically administered spesolimab or its excipients.

7. Any documented active or suspected malignancy or history of malignancy within 5 years prior to screening, except appropriately treated basal or squamous cell carcinoma of the skin or in situ carcinoma of uterine cervix.

8. Immediate life-threatening flare of GPP requiring intensive care treatment according to the investigator's judgement. Life-threatening complications include cardiovascular / cytokine driven shock, pulmonary distress syndrome, or renal failure.

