5.2.4.2 Adverse event collection and reporting

5.2.4.2.1 AE Collection

The investigator shall maintain and keep detailed records of all AEs in the patient files. The following must be collected and documented on the appropriate CRF(s) by the investigator:

- From signing the informed consent onwards until the individual patient's end of program (16 weeks after last dose of spesolimab, or at the time of withdrawal of participation): all AEs (serious and non-serious) and all AESIs.
- After the individual patient's end of program: the investigator does not need to actively monitor the patient for new AEs but should only report any occurrence of cancer and program drug-related SAEs and program drug-related AESIs of which the investigator may become aware of by any means of communication, e.g. phone call. Those AEs should however not be reported in the CRF.
- Upon patient re-entry into the program, the patient should be re-evaluated to ensure that eligibility criteria are still met and the overall program is still running in order to assess AEs (serious and non-serious) and AESIs.

Vital Status Data Collection

Patients who withdraw their consent to program participation, who agree to be contacted further but do not agree to physical visits, should be followed up as described in section [3.2.4.2](#), withdrawal from program treatment. Thus, for patients who withdraw their consent

but agree to be contacted by phone for a last follow-up assessment at 16 weeks after last drug intake, the investigator must report any occurrence of cancer, all deaths / fatal AEs regardless of relationship, and program drug-related SAEs and and program drug-related AESIs the investigator becomes aware of.

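### Protocol 6.1.3 closes follow-up at re-screening for a new flare and is silent on patients then not re-treated, which conflicts with the 16-week safety window

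*Protocol*

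**What the plan says.** Protocol 6.1.3 deals with a new flare inside the follow-up period in two steps. First, if the physician wishes to treat it with spesolimab, "eligibility needs to be assessed and agreed upon with the BI clinical team". Then, in case of re-entry, "the patient will end the current follow-up period, and restart the program from the screening for eligibility". The next sentence sets the conditions for treatment: "If eligibility criteria are met, and permission from BI is granted (see above), the patient can be treated again". Section 3.2.1 has the same requirement in general form: "Patients previously enrolled in this program presenting with a new episode of a GPP flare must be re-evaluated and meet eligibility criteria".

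Elsewhere the safety window is tied to the last dose. Section 5.2.4.2.1 requires collection from consent until "16 weeks after last dose of spesolimab, or at the time of withdrawal of participation): all AEs (serious and non-serious) and all AESIs". Section 7.1.1 defines treatment-emergent events over the same 16 weeks. Section 6.1.3 itself says that "participation in the program will end after conclusion of the" follow-up period counted from the last administration (its length is redacted there).

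SAP Table 6.1: 1 ends the on-treatment period at the earliest of three dates: 112 days after the last dose, the end-of-study visit, or the start of screening for the next flare. The third limit does not depend on a new dose being given.

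**The concern.** Read in order, 6.1.3 ends the current follow-up, restarts the patient at screening, and only then asks whether the patient may be treated. No visible text returns a patient to the original schedule if the criteria are not met or permission is refused. Such a patient has not withdrawn. The retention rule in flow chart footnote 3 covers premature discontinuation of treatment, and the 16-week contact in 3.2.4.1 covers a patient who wants to leave the program. Neither names a failed re-screening.

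The stake is safety follow-up. The flow chart places the visits up to V6/EoS in the follow-up period, and 6.1.3 has AEs and concomitant therapies recorded at visits. If a site took the closed follow-up as the end of the patient's program, 5.2.4.2.1 would leave only passive reporting of cancer and drug-related SAEs and AESIs, outside the CRF.

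The patients affected are unlikely to be a random subset. Grounds for failing re-screening in 3.2.3 include raised liver tests, infection, hypersensitivity, malignancy, acute demyelinating neuropathy and "Immediate life-threatening flare of GPP requiring intensive care treatment". These overlap in part with the AESIs in 5.2.4.1.4 and with SAEs, and TEAEs, SAEs and AESIs are the primary and secondary endpoints.

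**Working it through.** **Step 1: the nominal window.** The protocol gives 16 weeks (5.2.4.2.1, 7.1.1) and the SAP gives 112 days (Table 6.1: 1). 16 × 7 = 112, so the two documents agree.

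**Step 2: the rules applied to one patient.** Take a patient dosed once, re-screened w weeks later for a new flare, and not re-treated. The last dose is still the first one.

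| Source | What it implies for this patient |
|---|---|
| Protocol 6.1.3, re-entry paragraph | Follow-up ends at week w; nothing is stated after a failed re-screening |
| Protocol 6.1.3, end of participation | Runs to the end of follow-up after the last administration |
| Protocol 5.2.4.2.1 | All AEs and AESIs collected to week 16 |
| Protocol 7.1.1 | Events are treatment-emergent to week 16 |
| SAP Table 6.1: 1, third limit | On-treatment period ends at week w |

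The first and last rows stop at week w. The other three run on. The two groups cannot both be followed.

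**Step 3: how much of the window is exposed.** Days exposed = 112 − 7w; share = (112 − 7w)/112; patient-years = (112 − 7w)/365.25. The documents give no time to relapse, so w is assumed.

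| w (weeks) | Days exposed | Share of window | Patient-years |
|---|---|---|---|
| 2 | 112 − 14 = 98 | 87.5% | 0.268 |
| 4 | 112 − 28 = 84 | 75% | 0.230 |
| 8 | 112 − 56 = 56 | 50% | 0.153 |
| 12 | 112 − 84 = 28 | 25% | 0.077 |

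Under the SAP table these days leave the on-treatment period whether or not the AEs are collected. For data collection they are the most that could be lost, if a site stopped all contact at re-screening.

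**Step 4: effect on the results.** Under the SAP, AEs with onset after re-screening starts fall in a second screening phase and are not treatment-emergent. Counts of patients with an event can therefore only fall or stay the same.

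The SAP analyses the primary endpoint as a rate, 100 × n/T, where n is patients with the event and T is time at risk. Time at risk is censored at the end of the treatment period. Removing n′ patients with a first event and T′ years gives 100 × (n − n′)/(T − T′). This is lower than 100 × n/T only if n′/T′ exceeds n/T. The documents do not say which way that comparison goes.

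**The case against.** The strongest reply is that 6.1.3 has an earlier step. Eligibility is to be assessed and agreed with the sponsor before the re-entry paragraph begins, so follow-up might close only for patients already cleared. A patient with a known exclusion would then be stopped while follow-up is still running. This stands in part, because the wording is ambiguous. It does not remove the gap: the re-entry paragraph again makes eligibility and permission conditions after the restart, and 6.1.1 places the eligibility laboratory tests at screening, so a patient can fail after follow-up has closed. The third limit in the SAP table follows the same literal order.

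Other replies also carry weight:

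- Section 5.2.4.2.1 still requires collection to 16 weeks, and 5.2.4.2.3 requires follow-up of existing (S)AEs until they have resolved, are chronic or stable, or no further information can be obtained.
- An event that makes re-screening fail would itself be recorded, since the flow chart collects AEs at V1.
- Several follow-up visits may be held by phone or video, and examinations and laboratory tests at V3 to V6 are optional. What is at risk is mainly scheduled contact, not a fixed test battery.
- The exclusion criteria match the AESIs only loosely. AST, ALT or alkaline phosphatase above 3 × ULN alone excludes a patient. The hepatic AESI needs AST or ALT of at least 3 × ULN with bilirubin of at least 2 × ULN, or AST or ALT of at least 10 × ULN. Malignancy is not a listed AESI, although it is always serious.
- A figure next to the re-entry text in 6.1.3 is not shown, so the missing branch can be asserted only for the visible text.

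**Conclusion.** The point holds as a conflict between stated rules. Section 6.1.3 ends follow-up at re-screening, while 5.2.4.2.1 and 7.1.1 keep the safety window open to 16 weeks after the last dose. For patients re-screened but not re-treated, this puts the remaining scheduled contacts up to V6/EoS at risk. The exposed share is 75%, 50% or 25% of the window for re-screening at an assumed week 4, 8 or 12. The number of such patients cannot be derived, because the documents give no relapse or re-screening rate and set no recruitment goal.

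A reader might infer that these patients lose the rest of their 16-week observation, or that the reported rates are biased downwards. The documents support neither. Collection remains formally required, so the loss depends on how a site resolves the contradiction. Counts may be lowered, but for exposure-adjusted rates events and time are removed together and the direction is undetermined.

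The finding assumes that the redacted follow-up length in 6.1.3 matches the 16 weeks given in 3.2.4.1, 5.2.4.2.1 and 7.1.1. It is worth correcting because the affected patients may be those with safety findings and the correction is small.

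**What to change.** In Protocol 6.1.3, state that the current follow-up period ends only when the first dose for the new flare is given. Add that a patient who is re-screened but not re-treated stays on the original follow-up schedule, with AEs and concomitant therapies recorded to 16 weeks after the last dose. This brings 6.1.3 into line with 5.2.4.2.1 and 7.1.1.

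As a conforming change, let the third limit in SAP Table 6.1: 1 (start of screening for the next flare) apply only if the patient is actually re-treated. Otherwise AEs collected after a failed re-screening would still be left out of the treatment-emergent analysis. SAP section 3 applies the plan to three trials, so the revised table should be checked against each protocol.

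The cost is a short protocol amendment and one qualified line in the SAP. No dose, eligibility or treatment rule changes, and no visits are added beyond those already scheduled. The small downside is that re-screening procedures may overlap with a follow-up visit.

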7. STATISTICAL METHODS

Exploratory descriptive statistics of demographic and safety data will be presented.

7.1 PLANNED ANALYSES

Analyses will be based on the treated set (TS) which includes all patients who have been administered spesolimab.

7.1.1 Safety analyses

In general, safety analyses will be descriptive in nature and will be based on BI standards. No hypothesis testing is planned.

Adverse events will be coded using the Medical Dictionary for Drug Regulatory Activities (MedDRA). Standard BI summary tables and listings will be produced. Statistical analysis and reporting of adverse events will concentrate on treatment-emergent adverse events, i.e. all adverse events occurring between start of treatment and end of the REP, a period of 16 weeks after the last dose of program medication. Adverse events that start before first drug intake and deteriorate under treatment will also be considered as 'treatment-emergent'. All adverse events with an onset between start of treatment and end of the REP, a period of 16 weeks after the last dose of program medication, will be assigned to the on-treatment period for evaluation.

All treated patients will be included in the safety analysis.

Frequency, severity, and causal relationship of adverse events will be tabulated by system organ class and preferred term. after coding according to the current version of the Medical Dictionary for Drug Regulatory Activities (MedDRA) at database lock.

7.1.2 Efficacy analyses

8. INFORMED CONSENT, PROGRAM RECORDS, DATA PROTECTION, PUBLICATION POLICY, AND ADMINISTRATIVE STRUCTURE

The program will be carried out in compliance with the protocol, the ethical principles laid down in the Declaration of Helsinki, in accordance with the ICH Harmonized Guideline for Good Clinical Practice (GCP), relevant BI Standard Operating Procedures (SOPs), the EU directive 2001/20/EC / EU regulation 536/2014, the Japanese GCP regulations (Ministry of Health and Welfare Ordinance No. 28, March 27, 1997) and other relevant regulations. Investigators and site staff must adhere to these principles.

Standard medical care (prophylactic, diagnostic and therapeutic procedures) remains the responsibility of the treating physician of the patient.

The investigator will inform the sponsor immediately of any urgent safety measures taken to protect the program patients against any immediate hazard, as well as of any serious breaches of the protocol or of ICH GCP.

The Boehringer Ingelheim transparency and publication policy can be found on the following web page: trials.boehringer-ingelheim.com. The rights of the investigator and of the sponsor with regards to publication of the results of this program are described in the investigator contract. As a rule, no program results should be published prior to finalization of the Clinical Trial Report of the program.

The certificate of insurance cover is made available to the investigator and the patients and is stored in the ISF.

8.1 PROGRAM APPROVAL, PATIENT INFORMATION, INFORMED CONSENT

This program will be initiated only after all required legal documentation has been reviewed and approved by the respective Institutional Review Board (IRB / Independent Ethics Committee (IEC and competent authority (CA) according to national and international regulations. The same applies for the implementation of changes introduced by amendments. Prior to patient participation in the program, written informed consent must be obtained from each patient (or the patient's legally accepted representative) according to ICH-GCP and to the regulatory and legal requirements of the participating country. Each signature must be personally dated by each signatory and the informed consent and any additional patient-information form retained by the investigator as part of the program records. A signed copy of the informed consent and any additional patient information must be given to each patient or the patient's legally accepted representative.

The investigator or delegate must give a full explanation to program patients based on the patient information form. A language understandable to the patient should be chosen, technical terms and expressions avoided, if possible. The patient must be given sufficient time to consider participation in the program. The investigator or delegate obtains written

consent of the patient's own free will with the informed consent form after confirming that the patient understands the contents. The investigator or [redacted] delegate must sign (or place a seal on) and date the informed consent form. If a program collaborator has given a supplementary explanation, the program collaborator also signs (or places a seal on) and dates the informed consent.

Re-consenting may become necessary when new relevant information becomes available and should be conducted according to the sponsor's instructions. The consent and re-consenting process should be properly documented in the source documentation.

8.2 DATA QUALITY ASSURANCE

A risk-based approach is used for program quality management. It is initiated by the assessment of critical data and processes for program subject protection and reliability of the results as well as identification and assessment of associated risks. An Integrated Quality and Risk Management Plan or alternative plan, in line with the guidance provided by ICH Q9 and ICH-GCP E6, for fully outsourced trials, documents the rationale and strategies for risk management during program conduct including monitoring approaches, vendor management and other processes focusing on areas of greatest risk.

Continuous risk review and assessment may lead to adjustments in program conduct, program design or monitoring approaches. A quality assurance audit/inspection of this program may be conducted by the sponsor, sponsor's designees, or by IRB / IEC or by regulatory authorities. The quality assurance auditor will have access to all medical records, the investigator's program-related files and correspondence, and the informed consent documentation of this clinical program.

8.3 RECORDS

CRFs for individual patients will be provided by the sponsor. For drug accountability, refer to section [4.1.4](#).

8.3.1 Source documents

In accordance with regulatory requirements, the investigator should prepare and maintain adequate and accurate source documents and program records that include all observations and other data pertinent to the investigation on each program patient. Source data as well as reported data should follow the "ALCOA principles" and be attributable, legible, contemporaneous, original and accurate. Changes to the data should be traceable (audit trail). Data reported on the CRF must be consistent with the source data or the discrepancies must be explained.

The current medical history of the patient may not be sufficient to confirm eligibility for the program and the investigator may need to request previous medical histories and evidence of any diagnostic tests. In this case, the investigator must make one documented attempt to retrieve previous medical records. If this fails, a verbal history from the patient, documented in their medical records, would be acceptable.

If the patient is not compliant with the protocol, any corrective action e.g. re-training must be documented in the patient file.

For the CRF, data must be derived from source documents, for example:

- Patient identification: gender, year of birth (in accordance with local laws and regulations).
- Patient participation in the program (substance, program number, patient number, date patient was informed).
- Dates of patient's visits, including dispensing of program medication.
- Medical history (including program indication and concomitant diseases, if applicable).
- Medication history.
- Adverse events and outcome events (onset date (mandatory), and end date (if available)).
- Serious adverse events (onset date (mandatory), and end date (if available)).
- Concomitant therapy (start date, changes).
- Originals or copies of laboratory results and other imaging or testing results, with proper documented medical evaluation (in validated electronic format, if available).
- Completion of patient's participation in the program (end date; in case of premature discontinuation document the reason for it).
- Prior to allocation of a patient to a treatment into a clinical program, there must be documented evidence in the source data (e.g. medical records) that the program participant meets all inclusion criteria and does not meet any exclusion criteria. The absence of records (either medical records, verbal documented feedback of the patient or testing conducted specific for a protocol) to support inclusion/exclusion criteria does not make the patient eligible for the clinical program.

